## 6.6

For Part 3, blood samples for the assessment of [REDACTED] will be collected via cannulation or direct venepuncture in a suitable forearm vein at the time points indicated in Table 3 and will be sent by courier from [REDACTED] to [REDACTED]. The actual date and time of each blood sample will be recorded in the source documents and eCRF.

## STUDY PROTOCOL

**6.7 Total blood volume**

The approximate total blood volume taken per subject is given in Table 6 and Table 7.

**Table 6 Blood volumes – Parts 1, 2, 4 and 5**

Procedure	Sample volume (mL)	No. of samples	Total volume (mL)
Haematology	2	5	10
Biochemistry	5	5	25
Coagulation	4.5	5	22.5
Pharmacokinetics	2	18	36
		Overall total	93.5*

\* For subjects in Part 2, the amount of blood taken will be approximately twice this volume (blood sampling volumes for Treatment Periods 1 and 2 combined).

**Table 7 Blood volumes - Part 3**

Procedure	Sample volume (mL)	No. of samples*	Total volume (mL)*
Haematology	2	9 (11)	18 (22)
Biochemistry	5	9 (11)	45 (55)
Coagulation	4.5	9 (11)	40.5 (49.5)
Pharmacokinetics (MT-6345)	2	42	84
	2	15	30
	4	4	16
		Overall total	233.5 (256.5)

Abbreviations: [REDACTED]

\* The number of samples and total volume of blood for MT-6345 PK assessment are based on 14 days of dosing. Values in parentheses are applicable if dosing is extended to a maximum of 28 days.

The number and timing of samples may be amended following any interim PK parameter estimations. However, in this case, the total blood volume for each subject will not exceed 550 mL in a 4-week period. The first 0.5 mL of blood withdrawn via cannula will be discarded.

[REDACTED]

[REDACTED]

[REDACTED]

[REDACTED]

[REDACTED]

[REDACTED]

[REDACTED]

[REDACTED]

[REDACTED]

Europe/Mitsubishi Tanabe Pharma Europe Ltd

STUDY PROTOCOL

[REDACTED]

[REDACTED]

## STUDY PROTOCOL

**7 STUDY TREATMENT****7.1 Investigational Medicinal Product**

A description of the IMP is given in Table 8.

**Table 8 Investigational Medicinal Products**

	MT-6345	Placebo
Dosage form	Capsule	Capsule
Description	Swedish Orange Hard Capsule	Swedish Orange Hard Capsule
Unit dose strength	█ and █	Placebo to match MT-6345 █ and █
Dosage	Part 1: █ and Parts 2, 4 and 5: █ Part 3: █ and █	Not applicable
Route of administration	Oral	Oral
Treatment duration	Parts 1, 2, 4 and 5: single dose Part 3: multiple doses (Days 1 to 14 up to a maximum of 28)	Parts 1, 2, 4 and 5: single dose Part 3: multiple doses (Days 1 to 14 up to a maximum of Day 28)
Dosing instructions	Capsule(s) to be swallowed with at least 240 mL water	Capsule(s) to be swallowed with at least 240 mL water
Storage conditions	Store below 25°C	Store below 25°C

 Anticipated doses shown; may be modified based on emerging data.

MT-6345 capsules and placebo to match capsules will be manufactured by MTPC, Japan.

IMP will be imported, Qualified Person (QP) certified and shipped to █ by █, UK (trading as PCI). The Sponsor will provide the necessary documentation to show that the capsules have been manufactured and tested according to Good Manufacturing Practice together with a Batch Certificate, Certificates of Analysis and a transmissible spongiform encephalopathy Statement.

Individual subject doses will be packed in opaque high-density polyethylene bottles with desiccant-attached polypropylene caps, labelled and QP certified by █

All labelling will comply with applicable regulatory requirements.

**7.1.1 Compliance**

The IMP will be administered orally by designated qualified study personnel at █ who will check the subject's mouth and/or hands to confirm that the dose was swallowed. The Investigator, or suitably qualified staff member, will supervise the administration of IMP and the exact time of dosing will be recorded in the subject's source documents and eCRF.

**7.1.2 Shipping, receipt, handling and storage**

IMP will be shipped from █ to █ according to the required storage conditions.

On receiving a shipment of IMP at █, the Investigator or designee will conduct an inventory check and complete a supplies receipt document, the original of which will be retained at █; a copy must be returned to the Sponsor or designee as soon as possible. The Investigator or designee will maintain a record of all IMP received and returned.

STUDY PROTOCOL

At [REDACTED] the IMP will be stored below 25°C in a locked, restricted-access area. Refrigerated storage is not required. A temperature log recording the daily maximum/minimum temperature of the storage area will be maintained. Any IMP storage temperature deviations will be reported to the Sponsor as soon as possible.

**7.1.3 Dispensing**

The unblinded QP or designee at the clinical site will receive a copy of the final randomisation schedule for preparation of the IMP and preparation of the treatment allocation list.

On each dosing occasion, the Investigator or designee will provide the subject with the allocated dose. A record of the IMP dispensed to each subject will be maintained by the Investigator or designee in an Accountability Log.

**7.1.4 Accountability, returns and destruction**

During the study, the Investigator or designee will record the quantities of IMP dispensed and returned in an Accountability Log. IMP accountability (reconciliation) will be checked by the Sponsor. IMP is to be used only for this Protocol and not for any other purpose.

All unused IMP must be stored at [REDACTED] until permission has been given by the Sponsor for it to be returned to [REDACTED]

Following completion and review of all IMP accountability records and resolution of any discrepancies on-site, the Investigator will return all IMP to [REDACTED] for destruction according to their local procedures. Confirmation of destruction will be provided to the Sponsor.

**7.2 Subject identification**

Each subject will be assigned a unique Screening Identification Number by [REDACTED] Upon randomisation, each subject will also be assigned a unique Randomisation Number. Both the Screening Number and the Randomisation Number will be documented in the subject's source documents and eCRF.

Subjects who are withdrawn for non-treatment related reasons may be replaced at the discretion of the Sponsor and Investigator. The substitute subject will receive the same treatment assigned to the subject they replace. Subjects withdrawn as a result of treatment-emergent AEs (TEAEs) thought to be causally related to the IMP will generally not be replaced.

A list identifying the subjects by the Screening Number and Randomisation Number will be kept in the Investigator Site File.

**7.3 Procedures for assigning subjects to treatment groups**

Randomisation will be performed according to a computer-generated randomisation list, and subjects will be given a corresponding Randomisation Number.

Randomisation will take place after confirmation of inclusion and exclusion criteria prior to the first administration of IMP on Day 1.

The randomisation code will be produced by the Statistics Department at [REDACTED] Prior to the start of the study, a copy of the master randomisation code will be supplied to the pharmacy staff at [REDACTED] and the unblinded MTPE Clinical Supplies Department.

**7.4 Maintenance of the study blind and unblinding**

This is a double-blind study. Treatment assignment will not be known to the subjects, the Sponsor or the staff who are involved in the clinical evaluation of the subjects and the analysis of data. The randomisation schedule and disclosure envelopes will be generated by an unblinded statistician at

STUDY PROTOCOL

[REDACTED] according to [REDACTED] SOPs. The unblinded statistician will not be involved in any decisions relating to populations for analysis prior to unblinding.

For each subject, sealed treatment decode envelopes will be held in a secure area by the Investigator and Sponsor. The sealed code should not normally be broken for reasons other than safety or in an emergency. Should the Investigator wish to break the code for such reasons, he/she should ideally consult the Sponsor in advance. If this is not possible, the Investigator may break the code and document the date and reason for breaking the blind without prior discussion with the Sponsor. The Sponsor should be notified as soon as possible thereafter. If the blind is broken for any individual subject, the subject must be withdrawn from the study, and any procedures accompanying withdrawal should be performed (Section 4.5).

If the study stopping criteria appear to be met, the Sponsor will unblind individual subject allocations to confirm stopping criteria have been met. The specific mechanism for unblinding will be outlined in a separate document.

The Sponsor will authorise release of the unblinded randomisation list at the end of the study.

Prior to database lock and unblinding, all original randomisation materials, including the original final signed and dated randomisation schedule, will be held by the Quality Assurance (QA) department at [REDACTED]. The Data Sciences department will not have access to the randomisation schedule before database lock and unblinding.

A copy of the final randomisation schedule will also be made available to MTPE Clinical Supplies and the laboratory performing the bioanalysis to allow selective analysis of drug concentrations. The blind of the study will be broken after the study database has been locked and the safety population has been defined for that part. Any request for issue of the randomisation schedules must be made using a randomisation disclosure form.

MT-6345 and matching placebo capsules are identical in appearance. MT-6345 and matching placebo will be packaged identically and suitably labelled to maintain the blind.

---

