**Part 2: Food effect**

A single cohort from Part 1 (anticipated to be Cohort 3; [REDACTED] MT-6345) will be selected to return for a second treatment period to investigate the effect of food (after a Food & Drug Administration [FDA]-approved high-fat breakfast) on the PK of MT-6345. There will be a minimum of 15 days

Europe/Mitsubishi Tanabe Pharma Europe Ltd  
STUDY PROTOCOL

between the last dose administration in Part 1 and the first dose administration in Part 2. Subjects in Part 2 will receive the same dose (active or placebo) that they received in Part 1.

The dose and cohort selected for Part 2 will not be confirmed until safety, tolerability and PK data from the intended dose level in Part 1 has been reviewed and deemed acceptable. The intention is for all 8 subjects to be dosed sequentially on the same day.

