#### 4.5 Withdrawal of individual subjects

Subjects will be withdrawn from the study for the following reasons:

- The subject wishes to withdraw from further participation.
- The subject is significantly noncompliant with the Protocol.
- Continuing in the study would be detrimental to the subject's safety in the opinion of the Investigator, e.g.,
  - The subject experiences intolerable AEs or serious adverse events (SAEs)
  - The subject has clinically significant changes in safety parameters at any of the post-dose time points, as confirmed with a repeat assessment performed as soon as possible after the initial out-of-range result.
  - The subject has an increase in QTcF to  $\geq 500$  ms or increase of  $\geq 60$  ms from baseline (pre-dose on Day 1), as confirmed with three consecutive ECGs taken at least 5 minutes apart in a 30-minute period.
  - Development of any clinically significant liver dysfunction, as follows:
    - ALT or AST  $>8 \times$  ULN.
    - ALT or AST  $>5 \times$  ULN for more than 2 weeks.
    - ALT or AST  $>3 \times$  ULN in conjunction with elevated total bilirubin  $>2 \times$  ULN, or international normalised ratio  $>1.5$ .
    - ALT or AST  $>3 \times$  ULN with appearance of fatigue, nausea, vomiting, right upper quadrant pain or tenderness, fever, rash and/or eosinophilia ( $>5\%$ ).
  - Part 3 only: the subject has clinically significant changes to the corneal epithelium on the eye examinations conducted by a Consultant Ophthalmologist. Clinical significance will be judged by the Investigator.
- Pregnancy in a female subject.

In addition, a subject may be withdrawn at any time for reason(s) other than those listed here. If IMP is discontinued in a subject, then the subject may still undergo all other study procedures but will not receive the IMP.

If a subject is withdrawn from the study prematurely, the date the IMP is discontinued and the reason for withdrawal will be recorded on the electronic case report form (eCRF).

In case of withdrawal of a subject from the study, the Follow-up Visit assessments should be performed, as far as possible (Section 5.2.4).

Reporting as an SAE must be considered in cases where the AE has led to a withdrawal from the study or the withdrawal is for a safety reason and, therefore, may be medically important, in accordance with Section 8.2.

Any unresolved AE or SAE will be followed up according to Section 8.9.

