In the event that a subject elects not to return to the [REDACTED] for the Follow-up Visit, the Investigator must make every effort to contact the subject to review all AEs. In the event that a subject withdraws from the study at any time, the reason for withdrawal must be fully documented in the source documents and the eCRF. [REDACTED] personnel will document the

---

AEs and any other assessments in the source documents and eCRF and will make every effort to complete all required Follow-up Visit assessments.

Subjects who are withdrawn from the study following randomisation may not re-enter the study.

Subjects withdrawn from the study for non-treatment-related reasons may be replaced at the discretion of the Sponsor and Investigator. Replacement subjects will receive the treatments intended for the withdrawn subject.

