#### 5.2.4.2 Follow-up (Part 3)

Subjects will return to the clinic  $14 \pm 1$  days after last dose (336 hours after last dose) for a Follow-up Visit. The following assessments will be performed (refer to Table 3 for further details):

- Physical examination (including weight and BMI).
- All subjects will have an eye examination conducted by a Consultant Ophthalmologist at any time between day of last dose and the Follow-up Visit. Further details can be found in Section 6.5.1.
- Vital signs (including supine blood pressure, pulse rate, respiratory rate and oral body temperature).
- 12-lead ECG.
- Routine laboratory evaluations (haematology; biochemistry; coagulation; urinalysis).
- PK blood sampling for MT-6345.
- [REDACTED]
- AE and concomitant medication recording.

Subjects who are withdrawn from the study should, where possible, complete the procedures scheduled for the Follow-up Visit as soon as possible after withdrawal.

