#### 5.2.6 Unscheduled visits

An unscheduled visit is defined as any visit to [REDACTED] outside of the Protocol-specified time points due to safety reasons or when a repeated measurement is required (e.g., obvious measurement errors, measuring device failure, confirmation of out-of-range results), where the subject is seen by study personnel.

Additional unscheduled samples for safety assessments may be performed at the discretion of the Investigator, if deemed necessary. All unscheduled visits and assessments performed during the visits will be recorded in the eCRF.

---

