**8.5 Clinical laboratory abnormalities and other abnormal assessments**

Laboratory abnormalities which are clinically significant will be recorded as AEs or SAEs. The Investigator will exercise medical judgement in deciding whether abnormal laboratory values are clinically significant.

If an abnormal laboratory value or assessment is clearly related to a medically-defined diagnosis or syndrome, the diagnosis or syndrome will be recorded on the AE form, not the individual laboratory values.

All clinically significant abnormal laboratory results or assessments will be followed until they resolve (return to normal or baseline values) or until they are judged by the Investigator to be no longer clinically significant.

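### Protocol 7.4 requires study withdrawal after any individual code-break where stopping IMP would do, and the PK analysis set then drops any withdrawn subject, even one with an evaluable profile

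*Protocol*

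**What the plan says.** Protocol Section 7.4 expects codes to be broken normally only for safety or in an emergency. It then sets one consequence, with no exception by study part or dosing status: "If the blind is broken for any individual subject, the subject must be withdrawn from the study". It refers to Section 4.5 for the accompanying procedures.

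Section 4.5 also describes a less drastic route: "If IMP is discontinued in a subject, then the subject may still undergo all other study procedures but will not receive the IMP". For withdrawal from the study it asks for less: "In case of withdrawal of a subject from the study, the Follow-up Visit assessments should be performed, as far as possible".

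Only the Part 3 text (Section 5.2.4.2) says when that set is due: "Subjects who are withdrawn from the study should, where possible, complete the procedures scheduled for the Follow-up Visit as soon as possible after withdrawal". Section 5.2.4.1, for the single-dose parts, gives Day 15 ± 1 for the ordinary visit and no timing for withdrawn subjects. It also says that the cohort chosen for Part 2 skips the Follow-up Visit after its Part 1 dose.

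Some safeguards survive withdrawal:

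- Site staff "will make every effort to complete all required Follow-up Visit assessments" and must try to contact a subject who does not return (Section 4.5).
- "Additional unscheduled samples for safety assessments may be performed at the discretion of the Investigator, if deemed necessary" (Section 5.2.6).
- "All clinically significant abnormal laboratory results or assessments will be followed until they resolve" or are judged no longer clinically significant (Section 8.5), and unresolved AEs are followed under Section 8.9.

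The PK analysis set (protocol Section 10.2, repeated in SAP Section 5) is limited to subjects who complete the study, have no major emesis within 2 hours of dosing, and have evaluable PK parameters.

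**The concern.** Withdrawal from the study would be justified if it protected the subject or the data better than stopping IMP. In Parts 1, 2, 4 and 5 there is one dose per treatment period. Once it has been swallowed, neither action changes exposure to it. The one later dose at issue is the fed dose in Part 2 ("Subjects in Part 2 will receive the same dose (active or placebo) that they received in Part 1"), and stopping IMP prevents that equally well. The same holds for the remaining doses in Part 3.

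Section 4.5 already provides for withdrawal when continuing would harm the subject in the Investigator's opinion. What Section 7.4 adds, therefore, is subjects who could otherwise have stayed on schedule. Since codes are normally broken for safety, these are mostly people in whom scheduled observation is useful.

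The PK-set wording is a separate matter that applies to any withdrawal. An active subject withdrawn late, with a profile good enough for every planned parameter, is excluded because the study was not completed.

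**Working it through.** **1. The plan's own count.** Single-dose PK times (protocol Table 2 notes and Section 6.4) are pre-dose, 0.5, 1, 1.5, 2, 3, 4, 5, 6, 8, 12, 16, 24 and 48 h, which is 14 samples, plus 72, 120, 192 and 336 h, which is 4. The total is 14 + 4 = 18, and 18 × 2 mL = 36 mL, as in Table 6.

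**2. Other scheduled safety items after dosing and before Follow-up** (Section 5.2.2.1):

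- vital signs at 1, 2, 4, 8, 12, 24 and 48 h
- ECGs at 1, 2, 3, 8 and 24 h
- laboratory tests at 24 and 48 h

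**3. What is still to come at the time of a code-break.** The PK column includes the 336 h Follow-up sample. The other columns exclude the Follow-up set.

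| Break just after | PK samples left | Vital-sign sets | ECGs | Laboratory sets |
|---|---|---|---|---|
| 2 h | 13 | 5 | 3 | 2 |
| 24 h | 5 | 1 | 0 | 1 |
| 72 h | 3 | 0 | 0 | 0 |

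Under Section 7.4 each row is replaced by one Follow-up set, which contains at most one PK sample. After a break at 2 h, AUC0-24h can no longer be obtained; after a break at 24 h it is kept. In the cohort going on to Part 2 there is no Part 1 Follow-up sample, so each PK count is one lower: 12, 4 and 2. If only IMP were stopped, all these items could go ahead as scheduled.

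**4. PK-set consequence.** Each planned Part 1 cohort has 6 active subjects. Losing one leaves 5 in the PK summaries (SAP Section 8.3.2), unless the subject is replaced.

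For the power model (SAP Section 8.3.3), the half-width of the 95% CI for the slope is t(0.975, n−2) × s / √Sxx, where Sxx is the sum of squares of log dose about its mean. I compared n = 36 (six cohorts of 6) with n = 35, at the same s. Doses are redacted, so the spacings are assumptions. The first row takes the largest escalation factors allowed in Section 3.3.

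| Assumed steps between cohorts | Half-width ratio when the subject is lost from cohort 1, 2, 3, 4, 5, 6 |
|---|---|
| 5, 4, 3, 3, 3 | 1.039, 1.011, 1.002, 1.003, 1.012, 1.030 |
| all equal | 1.033, 1.012, 1.002, 1.002, 1.012, 1.033 |
| 5, 4, 2, 2, 2 | 1.047, 1.010, 1.001, 1.004, 1.011, 1.024 |

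Worked case (first row, cohort 1): Sxx falls from 161.88 to 150.24 and t rises from 2.0322 to 2.0345. The ratio is (2.0345 / 2.0322) × √(161.88 / 150.24) = 1.039.

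These three spacings give 0.1% to 4.7%. Steps of 5, 2, 2, 1.5 and 1.5 also respect the maxima and give 5.4% for the lowest cohort, so the range illustrates the size and is not a bound.

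**The case against.** **Rarity.** Code-breaks should be few, and Section 4.5 already withdraws many of the subjects concerned. No document gives a frequency. This stands and keeps the point small.

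**Blinding.** Withdrawing a decoded subject is a defensible way to protect causality judgements. The Investigator's causality assessment drives the study stopping rule (Section 4.7), and a reasonable possibility of causality is part of the dose-escalation rule (Section 4.6). Sentinels are one active and one placebo, so decoding one reveals the other. This is a real cost of the alternative. It does not show that withdrawal protects the subject, or that it protects PK concentrations, which are assay results.

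**Replacement.** Sections 4.5 and 7.2 allow replacement on the same treatment. It is discretionary, limited to non-treatment-related withdrawals, and generally not used for TEAEs thought to be caused by IMP. The fall from 6 to 5 therefore holds only where no replacement is made.

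**Stronger readings.** A reader might infer that safety follow-up ends at withdrawal. It does not: event-driven AE follow-up, contact efforts and unscheduled samples remain. What is lost is the scheduled detection of new changes. Sections 8.6 and 8.7 do end AE recording and SAE notification at withdrawal, unlike the opening of Section 8, but that is a side issue and nothing here depends on it.

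A reader might also infer an early Follow-up set and then nothing scheduled until Day 15. That borrows timing printed only for Part 3; for the single-dose parts the timing is unstated.

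Finally, a reader might carry the PK-set loss into the food, gender and race comparisons. SAP Section 10 dropped the mixed model and all Part 4 and 5 analyses, so no such effect can be claimed.

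**Conclusion.** The point holds as a minor one. Section 7.4 mandates the more drastic of two routes already in the protocol and prevents no exposure that the milder route would allow. Its cost per subject depends on timing. It is substantial just after 2 h (13 PK samples, or 12 in the cohort going to Part 2, with 5 vital-sign sets, 3 ECGs and 2 laboratory sets). By 72 h it is confined to PK sampling.

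The PK-set wording is an independent weakness that any withdrawal can trigger. If a withdrawn active subject is not replaced, a planned cohort falls from 6 to 5 and the slope interval widens by roughly 0.1% to 5%.

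These figures assume the code-break times shown, planned cohort sizes, unchanged residual variance and the dose spacings listed. The SAP reports that 44 subjects were actually randomised in Part 1, so the planned 36 active subjects are an illustration. SAP Section 1 also records that the study was terminated. Changing Section 7.4 can no longer alter its conduct, and only the PK-set definition can still affect the remaining analysis.

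**What to change.** - **Protocol 7.4:** make discontinuation of further IMP, including any Part 2 dose, the default after an individual code-break. With the subject's consent, continue all scheduled safety and PK assessments to the Follow-up Visit. Flag data collected after the break as unblinded. Section 4.5 still provides for withdrawal when continuing would be detrimental.
- **Protocol 10.2 and SAP Section 5:** define PK-set membership by evaluable PK parameters and the emesis rule, and remove study completion as a condition.

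The change is to wording only; the visits and samples are already scheduled. The price is that later AE and causality assessments in that subject are made unblinded. A flag in the listings discloses this but does not remove it from decisions under the stopping rules. For the study as it stands, the PK-set definition is the change worth making, before database lock.
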